1.0 Project Summary/Abstract

Acute and chronic inflammation both increase cardiovascular disease risk, especially with aging, which may be due to vascular dysfunction. Aging and inflammation also lead to increased oxidative stress, which impairs vascular function. During acute inflammation, endothelial function is altered differently in younger and older adults with decreases in endothelial function in younger, but not older adults. However, cardiorespiratory fitness is cardio-protective, impacting inflammation, vascular function, and oxidative stress. During acute inflammation, moderately fit older adults exhibit similar responses to younger adults, suggesting preserved endothelial reactivity. However, whether the protective mechanism is oxidative stress has not been confirmed. Furthermore, it is undetermined whether the vascular dysfunction is further propagated down the arterial tree during acute inflammation to the microvasculature. We will investigate these questions through 2 specific aims: 1) To determine if age and fitness moderate the vascular response to acute inflammation; 2) To determine if antioxidant administration eliminates vascular dysfunction during acute inflammation.

We will recruit 15 young low fit (18-35 years) and 30 older low or high fit (55-75 years) adults. An acute inflammatory bout will be induced by typhoid vaccination. The influence of oxidative stress will be assessed using an oral antioxidant. Baseline influences of the antioxidant on endothelial function will be assessed on Visit 1. Acute inflammation measures will be taken at baseline (Visit 2, prior to) and 24-hours after the vaccine (Visit 3). The antioxidant will be administered again on Visit 3.

We anticipate low fit older adults will have reduced endothelial responsiveness and microvascular reactivity compared to young and high fit older adults. Second, we anticipate the antioxidant will improve vascular function at baseline in low fit older adults. During acute inflammation, we anticipate improvement in vascular function to baseline levels in young and older high fit adults.

The results from this study will help to elucidate if fitness is a protective and preventive measure to ameliorate the detrimental cardiovascular response to acute inflammation. Thus, this study may provide health professionals with a behavioral intervention to reduce cardiovascular disease burden in the rapidly growing aging population.

2.0 Background/Scientific Rationale

Acute inflammation increases CV risk [1–4] with a higher prevalence of older adults experiencing adverse CV events[3]. Aging is associated with immunosenescence[5,6], rendering older adults more susceptible to infection[7] and may contribute to the higher mortality and acute CV events following acute inflammation in the elderly[1,2,8]. Indeed, infectious disease hospitalization and the concomitant inflammatory insult leads to an 8-fold increased risk of acute coronary syndromes in older adults within 15 days after admission[9].

[figure not shown]
Increased CV risk with acute inflammation may also stem from detrimental changes in endothelial function[10–12] and arterial stiffness[13–15]. Indeed, our laboratory has shown that endothelial function during acute inflammation decreases in younger, but not in older, adults [16,17]. Moreover, acute inflammation results in concomitant increases in arterial stiffness, a predictor of CV events. These large artery impairments during acute inflammation may be further propagated down the arterial tree to the microvasculature, altering microvascular reactivity. During a severe acute inflammation model, peripheral near-infrared spectroscopy (NIRS) evaluation of microvascular reperfusion is altered earlier than other systemic variables[18]. NIRS may therefore serve as an early detector of altered peripheral perfusion during acute inflammation. As such, identifying means to restore vascular reactivity during acute inflammation to levels seen in young adults may help attenuate CV risk in older adults.

Higher cardiorespiratory fitness and habitual physical activity are protective for many aspects of CV health[19,20] and appear to also be protective during acute inflammation. Recent data suggests voluntary running is protective against acute inflammation and the concomitant microvascular dysfunction in a mouse-model of sepsis[21].

Furthermore, population-based data suggests inadequate exercise (<1.07 MET h/day) is associated with a doubling of the risk of mortality during severe

acute inflammation (sepsis), independent of other risk factors[22]. Additionally, during acute inflammation, our group has shown moderately fit older adults 1) maintain vascular reactivity similar to that of younger adults[23], which may help protect maintenance of blood pressure and 2) do not experience increases in arterial stiffness as seen in low fit older adults.[15] These data suggest exercise has beneficial effects in clinical manifestations of inflammation and has shown potential cardioprotective effects during acute, low-grade inflammation.

Figure 1.

The protective effect of fitness in older adults is potentially due to lower oxidative stress. Aging alone increases oxidative stress which reduces nitric oxide bioavailability, impairing baseline endothelial function (Figure 1). In older adults, habitual physical activity maintains endothelial function to similar levels as young healthy adults[24,25] and increases antioxidant defense by reducing NADPH oxidase and nuclear factor- κ B (NF κ B) activity[26]. Salsalate administration inhibits NF κ B, reducing oxidative stress, and improving endothelial function[27]. Salsalate administration improves endothelial function in older, sedentary adults but not their trained counterparts or younger adults[28]. This supports the role of fitness in reducing oxidative stress with aging.

During *acute inflammation* in young adults, endothelium-independent vasodilation remains intact, indicating the change in endothelial function is likely due to reduced nitric oxide bioavailability and increased oxidative stress[11,12]. Increases in oxidative stress have been shown at 48 hours following a vaccination[10]. Additionally, ascorbic acid has partially resurrected forearm blood flow responses to acetylcholine during acute inflammation[11]. Since being physically active while aging maintains baseline levels of oxidative stress and endothelial function similar to that of young adults, changes in oxidative stress may explain the differing conduit endothelial responses between older low and high fit adults during acute inflammation. However, the mechanism of impairment has not been fully investigated. Antioxidant intake improves vascular function in older adults to similar levels of young adults, suggesting a role of oxidative stress[29,30]. Thus, ingestion of an antioxidant such as ascorbic acid may eliminate vascular dysfunction during acute inflammation.

To understand the vascular response to acute inflammation, an integrative approach must be applied to identify both the mechanism of vascular dysfunction and a potential therapeutic target to abrogate acute inflammation-induced vascular dysfunction. This study addresses both gaps of knowledge by investigating the role of oxidative stress and by recruiting participants based on training levels to effectively examine the effect of high fitness.

Relevance

[figure not shown]
CV disease is the leading cause of death in the United States and particularly burdens older individuals[31]. Aerobic exercise is recommended by the United States Physical Activity Guidelines, American Heart Association, and American College of Sports Medicine (ACSM) to improve quality of life, reduce risk of heart disease, diabetes, stroke, and osteoporosis, and improve immune function. If fitness moderates the effects of acute inflammation on vascular function, our study will provide insight into how physical activity and exercise interventions could reduce the risk of CV events during acute inflammation.

Preliminary Studies

Our laboratory has conducted a series of studies evaluating the effect of acute inflammation on cardiovascular function[15–17,32–34]. evaluated both cardiac and endothelial function during acute inflammation in younger and older adults[16,17,34]. These studies suggest age-associated differences in endothelial function, cardiac function, and blood pressure that may be detrimental to older adults[16,33,34]. We have shown that fitness, an indicator of chronic exercise, may exert protective effects. In older adults, high fitness protected from acute inflammation-induced arterial stiffening[15].

Recently our lab has shown that high fit older adults also have a similar endothelial response to acute inflammation as younger adults. The high fit older adults exhibit a greater reduction in flow-mediated dilation than older low fit adults. Fitness level did not influence the response in young adults (Figure 2)[23]. Additionally, we have collected pilot data on microvascular reactivity in young adults ($n=16$), showing no changes in tissue saturation index from baseline to 24h during acute inflammation in peak hyperemic response ($13.7\pm3.9\%$ to $13.8\pm2.9\%$) or reperfusion slope ($1.84\pm0.52\%/\text{s}$ to $1.83\pm0.49\%/\text{s}$).

Figure 2

3.0 Objectives/Aims

Aim 1: To determine if fitness moderates the vascular response to acute inflammation with aging. We hypothesize that during acute inflammation A) high fit older adults will have similar endothelial and microvascular reactivity as young adults; B) high fit older adults will have greater endothelial and microvascular reactivity than low fit older adults.

Aim 2: To determine if antioxidant administration eliminates vascular dysfunction during acute inflammation. We hypothesize A) at baseline, ascorbic acid will improve endothelial function only in low fit older adults; B) during acute inflammation, ascorbic acid will improve vascular function to baseline values in young and older high fit adults.

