4.0 Eligibility

4.1 Inclusion Criteria

- Males and females willing to provide informed consent
- 18-35 or 55-75 years of age
- Non-smoker
- No antioxidant/vitamin supplementation
- No use of anti-inflammatory medication within last 2 weeks
- Aerobically trained (defined as performing aerobic exercise on ≥ 4 days/week, for ≥ 30 minutes, for at least the past 3 months AND a $\text{VO2max} \geq 75^{\text{th}}$ age- and sex-specific percentile according to ACSM)

OR

Sedentary (defined as being involved in less than 30 minutes of moderately-intense physical activity per day, < 3 days/week AND a $\text{VO2max} \leq 50^{\text{th}}$ age- and sex-specific percentile according to ACSM)

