6.0 Study Design and Procedures

Study site

All study procedures except the vaccination will be conducted in the Integrative Physiology Laboratory at the University of Illinois at Chicago located at [name] in the Disability, Health and Social Policy building (DHSP). The typhoid vaccination will be administered by a registered nurse at the Clinical Research Center at UIC.

Design

A comparative, observational study design will be conducted with a group of 15 low fit young adults, 15 low fit older adults, and 15 high fit older adults, for a total of 45 research participants.

Subjects will participate in three study visits, with at least 72 hours between the first two visits, and exactly 24 hours between the last two visits. Menstruating females will be studied during the first 7 days of menses, or during the placebo phase if taking oral contraceptives. Participants will arrive to each visit having refrained from exercise, alcohol, and caffeine for 24h prior to each test day. Participants will be tested in the post-prandial (no food, only water) state (>10 hours) for all visits. (Figure 1)

[figure not shown]

Figure 1. Study protocol schematic

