12.0 Statistical Considerations

The data will initially be examined for normality violations, entry errors, and missing values. Entry errors will be corrected by double-checking with original data files. Non-normally distributed data will have an appropriate transformation applied to achieve normality (i.e. log transformation, square root, etc.).

All analyses will be adjusted for age, sex, and body mass index, which are all factors known to influence hemodynamic parameters. Additionally, due to multiple tests, a correction will be applied for multiple comparisons (α divided by the number of tests). Significance level will be set at $\alpha=0.05$, with a Bonferroni correction used to correct for multiple comparisons.

Aim 1: The effects of acute inflammation on endothelial and microvascular function will be tested with a two-way group (3) by time (2) repeated measures ANOVA (V2 and V3 baseline). We expect older high fit adults to have similar vascular reactivity as young adults, i.e. decreased FMD and NIRS reperfusion, suggesting that fitness maintains vascular reactivity during an inflammatory insult with age. If no difference in the response to acute inflammation is seen between low and high fit older adults (not expected), this would indicate fitness is not protective with age during acute inflammation.

Aim 2: The effects of ascorbic acid ingestion will be tested with a two-way group (3) by time (2) repeated measures ANOVA to determine if the antioxidant caused changes at Visit 1 (baseline) or Visit 3 (acute inflammation). A two-way group (3) and time (3) repeated measures (V2 baseline, V3 before and after Vit C) ANOVA will determine if the antioxidant attenuated endothelial function during acute inflammation. At baseline, we expect ascorbic acid to improve vascular function, i.e. increase FMD and NIRS reperfusion, in older low fit adults, with no changes seen in young or high fit older adults. During acute inflammation, we expect ascorbic acid to restore vascular function to baseline in young and older high fit adults. If ascorbic acid does not alter vascular function during acute inflammation, this would indicate another mechanism other than oxidative stress is contributing to vascular dysfunction.

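### Aim 1 compares high fit older with low fit young adults, so hypotheses 1A and 1B can both be met by additive effects, and age-by-fitness moderation is not estimable

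*Combined protocol and SAP*

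**What the plan says.** Section 3.0 gives Aim 1 as "To determine if fitness moderates the vascular response to acute inflammation with aging". Hypothesis 1A is that "high fit older adults will have similar endothelial and microvascular reactivity as young adults", and 1B that "high fit older adults will have greater endothelial and microvascular reactivity than low fit older adults". Neither states the fitness of the young adults.

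The fitness is given elsewhere. Section 1.0 says "We will recruit 15 young low fit (18-35 years) and 30 older low or high fit (55-75 years) adults", and Section 6.0 lists "15 low fit young adults, 15 low fit older adults, and 15 high fit older adults". Under Section 4.1, low fit means sedentary with a VO2max at or below the 50th age- and sex-specific percentile. High fit means aerobically trained and at or above the 75th.

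Section 12.0 tests Aim 1 with a "two-way group (3) by time (2) repeated measures ANOVA (V2 and V3 baseline" comparison). Group is one factor with three levels. Similarity of high fit older to young adults is read as "suggesting that fitness maintains vascular reactivity during an inflammatory insult with age". The same section adds a negative rule: if low and high fit older adults respond alike, fitness is taken not to be protective with age.

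Two other places bear on the point. Section 1.0 anticipates that low fit older adults will fall below both young and high fit older adults. The preliminary studies in Section 2.0 report that, in earlier work by the same laboratory on FMD, fitness made no difference to the response of young adults.

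**The concern.** Age crossed with fitness gives four groups, and this study has three. Because there are no high fit young adults, 1A compares people who differ in age and in fitness. Similarity could mean that fitness has removed the age effect. It could also mean that an unchanged age deficit has been offset by a fitness gain of about the same size, one that high fit young adults would show as well.

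Section 12.0 draws the first conclusion and sets out nothing that would separate it from the second. The age comparison at equal fitness, young low fit against older low fit, is anticipated in Section 1.0. Sections 3.0 and 12.0 do not make it a hypothesis, a planned contrast or a conclusion rule. At stake is a headline statement that fitness preserves reactivity with age. Section 9.0 says the results will inform the planning of later studies.

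**Working it through.** The plan gives no power, effect-size or sample-size figure to reproduce. The only total is 15 + 15 + 15 = 45, which agrees with 15 + 30 in Section 1.0.

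**1. Additive model.** Let a be the age deficit, f the gain from high fitness, and assume no interaction. The algebra is the same for the level at Visit 3 and for the size of the Visit 2 to Visit 3 change.

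| Group | Mean | Enrolled |
|---|---|---|
| Young low fit (YL) | m | 15 |
| Older low fit (OL) | m − a | 15 |
| Older high fit (OH) | m − a + f | 15 |
| Young high fit (YH) | m + f | none |

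- 1A contrast: OH − YL = f − a, which is near zero when f is near a.
- 1B contrast: OH − OL = f, which is positive for any f > 0.
- Age gap at equal fitness: YL − OL = YH − OH = a.
- Moderation: (OH − OL) − (YH − YL) = f − f = 0.

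**2. The same data under two truths.** Take a = f = 1 and m = 0. The observed means are YL 0, OL −1, OH 0.
- If YH = 1, the interaction is (0 + 1) − (1 − 0) = 0 and the age gap at high fitness is 1 − 0 = 1.
- If YH = 0, the interaction is (0 + 1) − (0 − 0) = 1 and the age gap at high fitness is 0 − 0 = 0.

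The three enrolled groups look identical in both cases.

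**3. Estimability.** With parameters for intercept, older, high fit and older × high fit, the three-group design matrix has rank 3 of 4. Estimable: OL − YL, OH − OL and OH − YL. Not estimable: the fitness effect in the young, the age gap at high fitness and the interaction. More participants in the same groups would not change this. Nor does the age adjustment in Section 12.0, because the ranges 18–35 and 55–75 do not overlap.

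**4. How close must f be to a?** No margin defines similar. With 15 per group, the 95% interval for a difference between two groups has half-width t(0.975, 28) × √(2/15) = 2.048 × 0.365 = 0.75 SD, so a sizeable gap can pass.

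The simulation used additive truth, 20,000 runs, two-sided t-tests and SD 1. 1A was scored as met if OH versus YL was not significant, and 1B if OH was significantly above OL. The SD, a, f and the Bonferroni count of three tests are assumptions.

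| a (SD) | f (SD) | Both met, α = 0.05 | Both met, α = 0.05/3 |
|---|---|---|---|
| 0.5 | 0.5 | 25% | 13% |
| 0.5 | 1.0 | 51% | 46% |
| 1.0 | 0.5 | 23% | 13% |
| 1.0 | 1.0 | 72% | 57–58% |
| 1.0 | 1.5 | 71% | 80% |
| 1.5 | 1.0 | 60% | 54% |
| 1.5 | 1.5 | 93% | 92% |
| 0.5 | 1.5 | 23% | 36% |

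The match need not be exact, but the chance is low when the effects are small or far apart.

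**5. NIRS.** The pilot in 16 young adults (Section 2.0) found no change at 24 hours: peak hyperemic response 13.7% to 13.8%, reperfusion slope 1.84 to 1.83 %/s. It is not split by fitness. If young adults do not respond on NIRS, high fit older adults could match them with no age effect present to protect against.

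**The case against.** The strongest reply is the preliminary finding that fitness did not change the young adults' response. If so, YH equals YL, low fit young adults can stand in for high fit ones, and 1A becomes a fair age comparison. For FMD this is real support, and it argues against the additive model on that outcome. But it comes from outside this study, the text gives no figures for it, the plan does not cite it as the reason for the design, and three groups cannot test it. The documents offer nothing comparable for NIRS, which Aim 1 also covers.

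A second reply is that Aim 1 may only mean that fitness alters the inflammatory response among older people. Section 1.0 words the aim as age and fitness each moderating the response, and the negative rule in Section 12.0 uses the like-for-like older comparison. On that reading OH versus OL answers the question, and this stands. It does not cover the positive conclusion in Section 12.0, which rests on similarity to young adults.

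A third reply is that Section 9.0 calls the study hypothesis generating. That excuses limited power. It does not make an unidentified quantity estimable.

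A reader might infer that the plan ignores the age comparison at equal fitness. Section 1.0 does not support that, since its expectation for low fit older against young adults is exactly this comparison. What is missing is its place in Sections 3.0 and 12.0.

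**Conclusion.** The point holds for Aim 1. 1A mixes age with fitness, 1A and 1B can both be met with no moderation, and age-by-fitness moderation is not estimable from these groups. The algebra and the rank result need no assumed figures. The frequencies, from 23% to 93% in the table at α = 0.05, depend on assumed effect sizes and on reading similar as non-significant.

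Two stronger readings are not supported. One is that additive effects always satisfy both hypotheses: 1A needs the fitness gain roughly to offset the age deficit. The other is that the design says nothing useful about fitness: the fitness effect in older adults and the age effect at low fitness are both estimable.

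For FMD, a claim that fitness removes the age effect is conditional on the preliminary-study result in young adults. For NIRS it has no support in the documents.

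**What to change.** In Sections 3.0 and 12.0:

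1. Specify two planned contrasts of the Visit 2 to Visit 3 change: young low fit versus older low fit (age), and older high fit versus older low fit (fitness). Count them in the Bonferroni correction. Estimate the age contrast without continuous age as a competing covariate, since the age ranges do not overlap.
2. Reword 1A as high fit older adults reaching the level of low fit young adults.
3. Draw a conclusion about age for an outcome only if the age contrast shows a difference, and word it as the effect of fitness in older adults relative to low fit young adults. The condition guards against similarity where there is no age difference, a real possibility for NIRS. It does not rule out the additive case, where the age difference is present (a > 0), so the narrower wording must do that work.
4. State that age-by-fitness moderation is not estimable, and that any stronger reading for FMD rests on the preliminary-study result in young adults.

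The cost is text and two contrasts on data already planned, with no extra participants. The downside is a narrower claim. A young high fit group of 15 (total 60) would make the interaction estimable, but only to about ± t(0.975, 56) × √(4/15) = 2.003 × 0.516 = 1.03 SD, so it is not needed for this fix.

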4.0 Eligibility

4.1 Inclusion Criteria

- Males and females willing to provide informed consent
- 18-35 or 55-75 years of age
- Non-smoker
- No antioxidant/vitamin supplementation
- No use of anti-inflammatory medication within last 2 weeks
- Aerobically trained (defined as performing aerobic exercise on ≥ 4 days/week, for ≥ 30 minutes, for at least the past 3 months AND a $\text{VO2max} \geq 75^{\text{th}}$ age- and sex-specific percentile according to ACSM)

OR

Sedentary (defined as being involved in less than 30 minutes of moderately-intense physical activity per day, < 3 days/week AND a $\text{VO2max} \leq 50^{\text{th}}$ age- and sex-specific percentile according to ACSM)

